#### 14.3.2 Grading of Adverse Events

This study will utilize the NCI Common Terminology Criteria for Adverse Events (CTCAE) Scale, Version 4.0 for AE grading (<http://ctep.cancer.gov/reporting/ctc.html>).

### 14.4 Follow-up of Adverse Events

All AEs and significant abnormal laboratory values must be followed up in accordance with the ICH Good Clinical Practice (GCP) guidelines, and other applicable regulatory requirements (eg, US Code of Federal Regulations [CFR]).

### 14.5 Relationship

The relationship of the event to pralatrexate will be assessed using the following definitions:

#### **Not Related:**

Evidence exists that the AE has an etiology other than pralatrexate (such as, pre-existing condition, underlying disease, intercurrent illness, or concomitant medications).

#### **Related:**

A temporal relationship exists between the event onset (or worsening) and the administration of pralatrexate. It cannot be readily explained by the patient's clinical state, intercurrent illness, or concomitant medications. In case of cessation or reduction of the dose, the event abates or resolves, and it reappears upon challenge.

It should be emphasized that ineffective treatment should not be considered as causally related in the context of AE reporting.

These criteria, in addition to good clinical judgment, should be used as a guide for determining the causal assessment.

## **14.6 Serious Adverse Events**

In the interest of patient care and to allow Allos to fulfill all regulatory requirements, any serious adverse event (SAE), regardless of causal relationship to pralatrexate, must be reported to Allos within 24 hours of knowledge of the event.

### **14.6.1 Definition**

SAEs are defined (CFR 312.32, ICH of Technical Requirements for Registration of Pharmaceuticals for Human Use E2A Guideline) as those AEs that meet any of the following criteria:

- Results in death.
- Is life-threatening: ie, any event that, in the opinion of the investigator, poses an immediate risk of death from that event.
- Requires inpatient hospitalization or prolongation of existing hospitalization (excluding hospitalizations for study therapy, disease-related procedures, or placement of an indwelling catheter, unless associated with other SAEs).
- Results in a persistent or significant disability/incapacity.
- Results in a congenital anomaly/birth defect.
- Includes important medical events that may not be immediately life-threatening or result in death or hospitalization but may jeopardize the patient or may require intervention to prevent 1 of the outcomes listed in this definition.

### **14.6.2 Serious Adverse Event Reporting**

- Any SAE that occurs from the time the study IC is obtained until randomization needs to be reported only if the event was related to a study procedure.
- Any SAE that occurs from randomization through 30 days after the last dose of pralatrexate or through 30 days after treatment discontinuation criteria are met for the Observation Arm must be reported to Allos within 24 hours of knowledge of the event. From 31 days after the last dose of pralatrexate, patients will continue to be assessed for SAEs that are related to pralatrexate.

- SAEs (regardless of causality) must be reported and the SAER faxed **within 24 hours of knowledge of the event to:**

Allos Therapeutics, Inc.  
Primary Contact: Clinical Drug Safety and  
Pharmacovigilance Department  
Phone: [REDACTED]  
Fax: [REDACTED] or [REDACTED]  
Email: [contact]

Allos may request additional information from the investigator to ensure the timely completion of accurate safety reports. Safety data that are critical to the reportability of an SAE, such as causality assessment and serious criteria, should be included in the initial fax for SAER. If omitted, a timely response to drug safety data queries received from Allos or an Allos designee is expected.

The investigator must take all therapeutic measures necessary for resolution of the SAE. Any medications necessary for treatment of the SAE must be recorded onto the concomitant medication section of the patient's CRF.

SAEs that are pralatrexate-related will be followed until resolution or returned to baseline/Grade 1, whichever is longer, or until it is determined that the outcome will not change with further follow-up.

Additionally, the SAE must be entered on the AE page(s) of the CRF. Follow-up SAERs need to be submitted to Allos as soon as additional information regarding the event becomes available (eg, diagnosis is made, laboratory or test results, event course, outcome, etc). The Allos CRA or designee will collect the original SAER from the site.

Allos/designee will be responsible for reporting SAEs to the regulatory authorities in accordance with applicable expedited reporting regulatory guidelines. The investigator is responsible for submitting SAEs to his/her Institutional Review Board (IRB)/Ethics Committee (EC)/Research Ethics Board (REB).

#### 14.6.3 Exclusions to Serious Adverse Event Reporting Requirements

The following are not considered SAEs:

- Situations where an untoward medical occurrence did not occur (eg, social and/or convenience admission to a hospital).
- Anticipated day-to-day fluctuations of pre-existing disease(s) or condition(s) present or detected prior to randomization that do not worsen.
- Elective hospitalizations solely for the initiation of subsequent therapy for the disease being studied.

## 14.7 Reproductive Risks

Pralatrexate must not be used during pregnancy or breastfeeding. Pre-menopausal females of childbearing potential will follow an approved, medically accepted birth control regimen (eg, birth control pills, intrauterine device, condoms, implants) or agree to abstain from heterosexual intercourse while participating in the study and for 30 days following the last dose of pralatrexate.

Males who are sexually active must agree to practice a medically acceptable barrier method contraceptive regimen (eg, condoms) or agree to abstain from heterosexual intercourse while receiving pralatrexate and for 90 days after the last administration of pralatrexate.

### 14.7.1 Pregnancy Notification

Pregnancies involving a study patient or a patient's partner that occur from the first dose of pralatrexate through 30 days after the last dose of pralatrexate must be brought to the attention of the treating physician immediately and reported to Allos within 24 hours after the investigator has gained knowledge of the event, using the Pregnancy Notification Form. The investigator must report any such event to Allos within 24 hours via telephone and via fax (see contact information in [Section 14.6.2](#)). Follow-up information regarding the outcome of the pregnancy will be requested by the Allos Clinical Drug Safety and Pharmacovigilance Department.

Treatment will be discontinued for all patients who become pregnant during participation in this study.

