  7. Females of childbearing potential (ie, excluding patients who are postmenopausal for at least 1 year [ $> 12$  months since last menses] or are surgically sterilized) must:
    - a. Have a negative serum pregnancy test within 14 days prior to randomization and
    - b. Agree to practice a medically acceptable contraceptive regimen from study treatment initiation until at least 30 days after the last administration of pralatrexate.
  8. Males who are sexually active, including those with a pregnant partner, must agree to practice a medically acceptable barrier method contraceptive regimen (eg, condoms) while receiving pralatrexate and for 90 days after the last administration of pralatrexate.
  9. Patient has given written informed consent (IC).

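### Partner pregnancies are notifiable only to 30 days after the last dose, although male patients must use contraception for 90 days; a pregnancy arising on days 31 to 90 need not be notified or followed.

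*Protocol*

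**What the plan says.** Protocol Section 14.7.1 governs "Pregnancies involving a study patient or a patient's partner". Both groups share one window: it covers those "that occur from the first dose of pralatrexate through 30 days after the last dose of pralatrexate must be brought" to the treating physician's notice, with a report to the sponsor within 24 hours of the investigator learning of the event. The sponsor then asks for information on the outcome.

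The contraception periods differ by sex:

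- **Men.** Section 14.7 requires a barrier method or abstinence "while receiving pralatrexate and for 90 days after the last administration of pralatrexate". Inclusion criterion 8, in Section 8.3 and in the Synopsis, gives the same 90 days.
- **Women of childbearing potential.** Section 14.7 requires contraception or abstinence "while participating in the study and for 30 days following the last dose of pralatrexate". Inclusion criterion 7 sets a minimum of 30 days after the last administration.

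After day 30, adverse event collection narrows to events related to pralatrexate (Sections 10.7.1 and 14.3.1). For serious events, Section 14.6.2 says: "From 31 days after the last dose of pralatrexate, patients will continue to be assessed for SAEs that are related to pralatrexate". Section 14.6.1 includes among the seriousness criteria an event that "Results in a congenital anomaly/birth defect"; pregnancy itself is not listed. The SAP has no provision on pregnancy.

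**The concern.** The protocol chose to collect partner pregnancies, and it asks men to avoid conception for 90 days after the last dose. It then stops requiring notification of partner pregnancies at day 30. The 30 days fit the female contraception period and appear to have been applied to partners without adjustment; no reason is given for treating the two sexes alike here when the contraception rules do not.

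At stake is information on exposed pregnancies. Section 4.3.1 warns of possible fetal harm, and Sections 3.2.2 and 4.3.1 report embryofetal toxicity in animals. Such pregnancies will be rare, so each report counts, and the normal outcomes matter as much as the abnormal ones because they form the denominator. Outcome follow-up under Section 14.7.1 belongs to the notification procedure. A pregnancy that is never notified is therefore not followed either.

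**Working it through.** No sample size, power or error-rate figure depends on this point. The check is a comparison of windows, all counted from the last dose of pralatrexate.

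| Group | Contraception required through | Pregnancy notifiable through | Gap |
|---|---|---|---|
| Female patients | day 30 (inclusion criterion 7 minimum; Section 14.7) | day 30 (Section 14.7.1) | 30 - 30 = 0 days |
| Partners of male patients | day 90 (inclusion criterion 8; Section 14.7) | day 30 (Section 14.7.1) | 90 - 30 = 60 days |

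The male gap runs from day 31 to day 90 inclusive: 90 - 31 + 1 = 60 days.

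**Does another passage close it?**

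1. Sections 10.7.1 and 14.3.1: from day 31 only pralatrexate-related adverse events are recorded. A pregnancy with a normal outcome is not captured.
2. Section 14.6.2: assessment for related serious events continues after day 30 with no stated end date. Together with the congenital-anomaly criterion in Section 14.6.1, this gives an abnormal outcome a possible route. It needs an adverse outcome and a judgement of relatedness, and it is framed around the study patient rather than the partner.
3. Sections 10.8 and 10.9: patients stay in follow-up for up to 7 years from randomization, and related adverse events are recorded at the Section 10.8 visits. Sites would generally still be in contact with patients, but neither section asks about pregnancy.

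No passage found requires notification of a partner pregnancy arising on days 31 to 90.

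**A loose term.** Section 14.7.1 does not say whether a pregnancy occurs when it is conceived or when it is detected. If conception is meant, one conceived by day 30 and found later is notifiable. If detection is meant, a pregnancy conceived late in treatment but found after day 30 also falls outside.

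**How large is 60 days?** It is 60/90 = 67% of the post-dose male contraception period. That period also includes time on treatment, when partner pregnancies are notifiable. Treatment lengths here are assumptions:

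- two years, the planned maximum: 60/(730 + 90) = 60/820, about 7%;
- three months: 60/(90 + 90) = 60/180, about 33%.

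These are shares of time, not expected numbers of pregnancies. The documents give no count of male patients, of sexually active men, or of expected pregnancies.

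**The case against.** The strongest reply is that contraception and notification are separate rules, and no passage says that their durations must be equal. The male requirement is a precaution. The protocol does not call the 90 days a risk period, gives no data on exposure through the father, and reports low mutagenic potential. The fetal-harm warning concerns administration to a pregnant woman. Men must also use a barrier method or abstain throughout the 60 days, so a pregnancy would arise only from non-adherence or method failure. All of this stands. It makes the point an alignment of two rules rather than a flat contradiction, and it means few events.

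It does not remove the gap. The protocol itself brings partners within the notification rule and sets the longer period for men; it gives no reason for ending notification at day 30.

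Four stronger readings are tempting, and the documents do not support them:

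- **Everything after day 30 is lost.** A related serious event, including a related congenital anomaly, is still assessed under Section 14.6.2.
- **Follow-up of serious adverse events must be lengthened too.** For related events it already has no end date after day 30. Writing in 90 days could be read as a new limit.
- **The secondary safety objective is compromised.** Its endpoints are treatment-emergent adverse events and laboratory changes (Protocol Section 15.2.2; SAP Section 4.3), and the safety analysis set contains randomized patients only. A partner's pregnancy enters neither.
- **Two-thirds of the window, across the 366 patients planned for pralatrexate, measures the loss.** Neither figure estimates a number of pregnancies.

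**Conclusion.** The mismatch holds. Followed as written, Section 14.7.1 leaves a partner pregnancy arising on days 31 to 90 without required notification or outcome follow-up, apart from the partial route for related serious events. The gap is 60 days for partners of male patients and none for female patients, taking 30 days as the female post-dose period.

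The consequence is confined to completeness of pregnancy safety reporting. It rests on the protocol's own male contraception period, not on any evidence in the documents of harm through paternal exposure. No view is taken on which contraception duration is right. This is a cheap improvement worth making, not a threat to the trial's conclusions.

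**What to change.** Reconcile Section 14.7.1 with Section 14.7 and inclusion criteria 7 and 8. Define the notification and outcome follow-up window by reference to the contraception period: for female patients, through the end of the period required of women; for partners of male patients, through the end of the period required of men. Tying the windows together this way keeps them aligned if a contraception period is later amended. The same sentence can state whether a pregnancy is dated by conception or by detection. Leave the follow-up of serious adverse events in Section 14.6.2 as it is.

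The cost is one revised sentence, a matching edit to the Pregnancy Notification Form, and a few extra reports at most. No visit, dose or analysis changes.

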## 15 STATISTICAL PLAN

### 15.1 Objectives

#### Primary

- Determine the efficacy of pralatrexate compared to observation when administered to patients with previously undiagnosed PTCL who have achieved an objective response after completing at least 6 cycles of CHOP-based treatment.

#### Secondary

- Determine the safety of pralatrexate when administered following a course of CHOP-based treatment to patients with previously undiagnosed PTCL.

### 15.2 Endpoints

#### 15.2.1 Efficacy Endpoints

##### Primary

- PFS and OS.

##### Secondary

- Objective response (CR or PR) to pralatrexate versus observation.

The primary analyses of PFS and response will use the central review tumor assessments per IWC without using PET. Additional analyses of PFS and response will use IWC, including PET, and investigators' assessment of response.

#### 15.2.2 Safety Endpoints

The safety endpoints include:

- Incidence and severity of treatment-emergent AEs.
- Changes in laboratory values.

### 15.3 Analysis Population

#### 15.3.1 Primary Analysis Set/Intent-to-treat Analysis Set

The primary efficacy set, also referred to as the intent-to-treat population, includes all randomized patients. Each patient will be included in the treatment group assigned at randomization, regardless of the treatment received. This analysis set will be used for the primary analyses of all efficacy endpoints.

### 15.3.2 Safety Analysis Set

The safety analysis set consists of all patients randomized to the Pralatrexate Arm who receive at least 1 dose of pralatrexate plus all patients randomized to the Observation Arm who do not discontinue the study within 3 days of randomization. This analysis set will be used for the primary analyses of all safety endpoints.

### 15.3.3 Interim Analyses Sets

One analysis of PFS, and 2 formal interim analyses and a final analysis of OS will be performed. The first analysis will be performed when both 280 PFS events and 128 OS events have occurred. The only analysis for PFS will be performed at this first analysis, and will be assessed at the 0.05 level of significance. If PFS is significant at the 0.05 level, an analysis will be conducted on OS at this time. If PFS is not significant at the 0.05 level, the study will be stopped. Two additional analyses of survival will be performed when approximately two-thirds of 385 deaths, and all 385 deaths have occurred, respectively.

## 15.4 Sample Size

A total of 549 randomized patients are planned for this study.

Outcome data for patients with T-cell lymphoma who receive first-line CHOP is limited. A retrospective study of the International T-Cell Lymphoma Project demonstrated a 5-year OS rate of 32% and a 5-year FFS rate of 20% for patients with PTCL-NOS, with widely varying results for other subtypes. Median OS for these patients did not seem to be a function of whether the patient received an anthracycline-based induction therapy. In a retrospective evaluation of 96 patients diagnosed within the Non-Hodgkin's Lymphoma Classification Project, Rudiger et al report a similar finding, with 5-year OS and FFS rates of 26% and 20%, respectively, for PTCL patients treated with a doxorubicin-containing regimen. Per Figure 1 of the Rudiger publication, the estimated median FFS in these patients is approximately 6 months.

Reports of response rate to first-line CHOP-based regimens in patients with PTCL are also available. Gallamini, et al (2007) conducted a small study (n = 24 evaluable) evaluating CHOP plus alemtuzumab administered every 4 weeks for a total of 28 weeks. They observed an overall response rate of 75% (71% CR, 4% PR). In a separate report, Gallamini, et al performed a retrospective analysis of 385 patients with PTCL-U, with the majority (78%) receiving chemotherapy containing anthracycline. They reported an overall response rate of 74% (53% CR, 21% PR) in the 372 evaluable patients. Mercadal and colleagues reported on a series of 41 patients ≤ 65 years old who were planned to receive 6 cycles of intensive chemotherapy (high-dose CHOP alternating with etoposide, methylprednisolone, cytarabine, and cisplatin [ESHAP]) followed by autologous stem cell transplantation, if in response. Twenty-eight patients (68%) received the planned 6 courses of therapy, 6 (15%) patients received 5 courses of therapy, and 7 (17%) received less than 5 courses. Following the chemotherapy phase, the CR rate was 49% and the PR rate was 10%. Kim and collaborators administered CHOP plus etoposide and gemcitabine to a cohort

of 26 first-line PTCL patients. The median number of cycles administered was 4, and the overall response rate was 77% (62% CR, 15% PR). Abouyabis and colleagues performed a meta-analysis of non-ALCL PTCL patients receiving anthracycline-based chemotherapy in the first-line setting. A total of 31 studies were identified involving a total of 1996 patients. The overall CR rate was 55% and the 5-year OS rate was 37%.

Across all of these reported studies, approximately 50% of patients achieve a CR to first-line CHOP, with an additional 10-20% achieving a PR. Furthermore, the 5-year PFS is approximately 20%, with a median PFS of approximately 9 months in all patients. For the PDX-017 study, we assume one-third of patients will have disease refractory to CHOP, and that the median PFS in these patients will be 3 months. Coupled with an overall median PFS of 9 months, and assuming exponentially distributed PFS, this implies the median PFS in patients who respond to CHOP is approximately 16 months. Subtracting out 6 months for CHOP administration and washout prior to randomization results in an estimated 10 month median PFS for the Observation Arm patients in this study.

The sample size is based on comparing the treatment groups with respect to the primary efficacy endpoints of PFS and OS. Assuming proportional hazards, a true hazard ratio (HR) on OS of 0.73, and a 2:1 randomization (treatment:observation) with a total of 549 patients (366 in the treatment group vs 183 in the observation group), a total of 385 OS events (deaths) will provide at least 80% power to show  $HR < 1.00$  using a 2-sided stratified log-rank test at a 0.05 significance level ( $\alpha = 0.05$ ), assuming an accrual period of 54 months and a follow up period of 30 months. For a HR on PFS of 0.67, and a 2:1 randomization (treatment:observation), a total of 280 PFS events (PD + deaths) will provide at least 80% power to show  $HR < 1.00$  using a 2-sided stratified log-rank test at a 0.05 significance level ( $\alpha = 0.05$ ).

## 15.5 Stratification

Patients meeting randomization eligibility criteria will be randomized 2:1 to the Pralatrexate Arm or the Observation Arm according to a permuted block design, balancing within the following stratum.

- Response per investigator at completion of CHOP-based therapy (CR vs PR)

## 15.6 Analysis Plans

### 15.6.1 Interim Analyses of OS

Two formal interim analyses and a final analysis of OS will be performed. The first interim analysis will be performed when both 280 PFS events and 128 OS events have occurred. The only analysis for PFS will be performed at this time, and will be assessed at the 0.05 level of significance. If PFS is significant at the 0.05 level, an interim analysis will be conducted on survival at this time. If there are 128 OS events, or 1/3 of the information of 385 deaths, included in the first interim analysis of OS, the level of significance ( $\alpha$ ) would be 0.0002, according to O'Brien and Fleming. If PFS is significant, a test for futility

of OS will not be conducted at the first interim analysis since such a result could not occur. The second interim analysis for OS will be performed when two-thirds (256) of the survival events have occurred, at the 0.013 level of significance. The HR stopping bound for futility at this interim analysis will be 1.05 (95% confidence interval [CI]: 0.80, 1.29). If the HR for OS is greater than 1.05, the study will be stopped. The final analysis for survival will be performed when 385 OS events have occurred, at the 0.046 level of significance.

A DMC will periodically review safety data at regularly scheduled meetings and at the same time as each interim analysis of efficacy. The first formal safety review will occur when approximately 100 patients have been randomized and completed at least 8 weeks post-randomization pralatrexate/observation or have discontinued.

At each interim analysis for survival, the study may be stopped for overwhelming evidence of futility or superiority according to specified boundaries. The DMC may also make recommendations regarding adjustments to the sample size, if they are warranted.

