#### 15.6.2 Final Analyses of Efficacy Endpoints

The primary efficacy analysis on PFS will be performed when approximately 280 PFS events and 128 OS events have occurred. This is estimated to occur approximately 48 months after the first patient is randomized. Allos will set a data cut-off date for the primary efficacy analyses in anticipation of 280th PFS event and 128th OS event. The primary efficacy analysis on OS will be performed when approximately 385 OS events have occurred.

A step-down procedure will be used for analyzing the co-primary endpoints of PFS and OS. If the PFS endpoint is significant at the 0.05 level the OS endpoint will be tested at an overall significance level of 0.05. However, if the PFS endpoint fails to show significance, the study will be stopped and OS will not be tested. The study will meet its primary objective if both the PFS and OS endpoints are significant. The interim analysis for OS will be implemented using the error-spending approach of Lan and DeMets according to the unified family approach with boundary relationships of O'Brien and Fleming for early stopping to reject the null hypothesis (superiority). The boundaries for early stopping due to failure to reject the null hypothesis (futility) will be determined according to the unified family approach with boundary shape parameters on the sample mean scale that result from choosing  $P = 2.0$  (all R and A parameters in the unified family approach set equal to zero).

The primary analyses of PFS and objective response will use the central review tumor assessments per IWC without using PET. Additional analyses of PFS and response will use IWC, including PET, and investigators' assessment of response. Additional details regarding central review will be provided in the reviewer's charter.

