3.3 Interim Analyses

A step down procedure will be used for analyzing the co-primary endpoints of PFS and OS. If the PFS endpoint is significant at the 0.05 level the OS endpoint will be tested at an overall significance level of 0.05. However, if the PFS endpoint fails to show significance, the study will be stopped and OS will not be tested. The study will meet its primary objective if both

the PFS and OS endpoints are significant. The interim analyses for OS will be implemented using the error-spending approach of Lan and DeMets according to the unified family approach with boundary relationships of O'Brien and Fleming for early stopping to reject the null hypothesis (superiority).^{8,9} The boundaries for early stopping due to failure to reject the null hypothesis (futility) will be determined according to the unified family approach with boundary shape parameters on the sample mean scale that result from choosing $P = 2.0$ (all R and A parameters in the unified family approach set equal to zero).¹⁰

There will be 1 final analysis of PFS, and 2 interim and 1 final analyses of OS. The first interim analysis of OS will be performed at the same time as the PFS analysis. The first interim analysis will be performed when both 280 PFS events and 128 OS events have occurred. The only analysis for PFS will be performed at this first analysis point, at the 0.05 level of significance. If PFS is significant at the 0.05 level, the first interim analysis will be conducted on survival at this time. If the PFS analysis is not significant at the 0.05 level, the study will be stopped. If there are 128 OS events, or one-third of the information of 385 deaths, included in the first interim analysis of OS, the level of significance (alpha) would be 0.0002, according to O'Brien and Fleming.^{8,9} If PFS is significant, a test for futility of OS will not be conducted at the first interim analysis since such a result could not occur. The second interim analysis for OS will be performed when two-thirds (256) of the survival events have occurred, at the 0.013 level of significance. The HR stopping bound for futility at this interim analysis will be 1.05 (95% confidence interval [CI]: 0.80, 1.29). If the HR for OS is greater than 1.05, the study will be stopped. The final analysis for survival will be performed when 385 OS events have occurred, at the 0.046 level of significance.

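### The 0.013 level for the second OS interim does not match the named Lan-DeMets O'Brien-Fleming spending, which gives 0.0119 at 256 of 385 deaths

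*Protocol*

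**What the plan says.** Protocol 15.6.2 sets the overall error for OS: "If the PFS endpoint is significant at the 0.05 level the OS endpoint will be tested at an overall significance level of 0.05". Protocol 15.4 sizes the OS comparison "using a 2-sided stratified log-rank test at a 0.05 significance level". The method for the interim looks, also in 15.6.2, is the "error-spending approach of Lan and DeMets according to the unified family approach with boundary relationships of" O'Brien and Fleming.

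Protocol 15.6.1 then gives three nominal levels.

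- First look: "If there are 128 OS events, or 1/3 of the information of 385 deaths, included in the first interim analysis of OS", the level "would be 0.0002, according to" O'Brien and Fleming. This level is conditional on the death count.
- Second look: "The second interim analysis for OS will be performed when two-thirds (256) of the survival events have occurred, at the 0.013 level of significance".
- Final look: 0.046 at 385 deaths.

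The second and final levels carry no such condition. SAP 3.3 gives the same method and the same three levels, with the second look "when two-thirds (256) of the survival events have occurred, at the 0.013 level of significance".

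**The concern.** The method, overall level, sidedness and death counts are all stated, so each nominal level can be recomputed from the documents alone. Two of the three agree with the named method and the middle one does not. The middle one is the threshold at which the Data Monitoring Committee could recommend stopping for superiority on OS, a co-primary endpoint. A two-sided p value between 0.0119 and 0.013 at that look would cross the printed level but not the boundary of the named method, and neither document says which prevails. That should be settled before anyone sees the data.

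**Working it through.** **Inputs.** Overall two-sided error 0.05, that is 0.025 per side (Protocol 15.4 and 15.6.2). Looks at 128, 256 and 385 deaths (Protocol 15.6.1, SAP 3.3). Information fractions: 128/385 = 0.3325, 256/385 = 0.6649, and 1. Allocation 2:1 (Protocol 15.4).

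**Step 1: cumulative error allowed.** The standard O'Brien-Fleming-type spending function, per side, is 2 × [1 − Φ(z(0.0125)/√t)], with z(0.0125) = 2.2414. Doubled to two-sided, it gives:

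- t = 0.3325: 0.0002
- t = 0.6649: 0.01197
- t = 1: 0.0500

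**Step 2: boundaries.** Each boundary is solved in turn, by numerical integration of the joint normal distribution of the log-rank statistics, so that the cumulative crossing probability equals the value in step 1.

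| Look (deaths) | z | Two-sided level | Stated |
|---|---|---|---|
| 128 | 3.716 | 0.0002 | 0.0002 |
| 256 | 2.515 | 0.0119 | 0.013 |
| 385 | 1.993 | 0.0463 | 0.046 |

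The plan's first and final figures are reproduced. The second is not.

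**Step 3: other readings of the design.**

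- Exact thirds instead of 256/385: second level 0.0120.
- First look omitted: 0.0120.
- Classical O'Brien-Fleming: 0.0005, 0.0140, 0.0451. Its first level contradicts the stated 0.0002.
- Spending function applied to 0.05 and then halved: 0.0007, 0.0160, 0.0439.

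None gives 0.013 at 256 deaths. The named function reaches 0.0127 at 260 deaths and 0.0131 at 262.

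**Step 4: overall two-sided error of each printed set, by the same integration.**

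| Levels | Overall error |
|---|---|
| 0.0002 / 0.013 / 0.046 (as stated) | 0.0502 |
| 0.0002 / 0.013 / 0.0457 | 0.0500 (0.04996) |
| 0.0002 / 0.012 / 0.046 | 0.0498 |
| 0.0002 / 0.0119 / 0.046 | 0.0497 |
| 0.0002 / 0.0119 / 0.0463 | 0.0500 |

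A simulation of 20 million paths gave 0.05025 for the stated set (standard error 0.00005). Treating the futility bound of HR 1.05 as binding leaves it at 0.0502. Adding the three levels (0.0592) does not give the type I error, because the looks are correlated.

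At the second look itself, the stated set has spent 0.01307 against the 0.01197 allowed: 0.01307/0.01197 = 1.09, about 9% over.

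**Step 5: effect on the stopping threshold.** With 2:1 allocation the log hazard ratio has standard error 1/√(256 × 2/9) = 1/7.542.

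- Level 0.013: z = 2.484, HR = exp(−2.484/7.542) = 0.719.
- Level 0.0119: z = 2.515, HR = exp(−2.515/7.542) = 0.716.

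**The case against.** The printed levels are rounded, and the overall excess depends on reading them as exact. A final level of 0.0457 also prints as 0.046 and, with 0.013 kept, brings the total back to 0.0500. This stands. A reader might infer from the sum in step 4 that the plan fails to control the OS error at 0.05, but the printed figures do not establish that.

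A reader might also infer that the inflation grows if the first look comes after 128 deaths, since it waits for 280 PFS events as well and the later levels are written as fixed. The documents do not support a figure for this. They give no control-arm OS median and no expected death count at that look. The scenario also assumes that spending is followed at the first look and abandoned afterwards, whereas the plan commits to "using the error-spending approach of Lan and DeMets" for the OS interims generally. That commitment already implies recomputation at the observed information, so a sentence saying so would clarify the method and would not add to it.

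The benchmark itself can be questioned. No spending function is written out, the wording also invokes the unified family, and 0.013 lies between the Lan-DeMets value (0.0119) and the classical one (0.0140). However, the stated 0.0002 fits only the first of these designs, and neither gives 0.013 at 256 deaths.

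Finally, the practical effect is slight. The probability that the second-look p value falls between 0.0119 and 0.013 in favour of pralatrexate is about 0.0006 under no effect and about 1.2% under HR 0.73. This also stands, and it limits the importance of the point without making 0.013 correct.

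**Conclusion.** The 0.013 in Protocol 15.6.1 and SAP 3.3 is inconsistent with the method both documents name. The value at 256 of 385 deaths is 0.0119, which prints as 0.012, and rounding cannot turn it into 0.013. The consequence is an interim efficacy threshold that is slightly too lenient: HR about 0.719 where the named method gives about 0.716. The overall two-sided error as printed is about 0.0502, an excess of about 0.0002 that lies within the rounding of the final level, so this is not a material loss of error control. Sample size, event targets and the PFS analysis are unaffected.

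The conclusion assumes the standard O'Brien-Fleming-type spending function with 0.025 per side, looks at exactly 128, 256 and 385 deaths, and the usual normal approximation for the log-rank statistic. The agreement of the other two stated levels supports the choice of function. The point is minor, but it concerns a decision threshold and is easily corrected.

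**What to change.** In Protocol 15.6.1 and SAP 3.3, replace 0.013 by 0.012 (0.0119). In the same places, add a sentence saying that the second and final OS levels, like the first, are planning values and will be recomputed from the spending function at the actual number of deaths. It would help to write out the spending function there.

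Keeping 0.013 and stating the final level as 0.0457 would also hold the overall error at 0.05, but the second look would still disagree with the named method, so correcting the interim level is preferable.

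The cost is one number and one sentence in each document, and a marginally stricter threshold at the second look.
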